5.3 Selection Criteria

Inclusion Criteria:

- Subject (or legally authorized representative) provides written informed consent prior to the initiation of any study procedures.
- Subject understands and agrees to comply with planned study procedures, including using the diary.
- Subject agrees to the collection of nasopharyngeal swabs and venous blood per protocol.
- Subject is male or non-pregnant female adult ≥18 years of age at time of consent.
 - Women with a history of menstruation must agree to use two methods of contraception, at least one of which is highly effective, for the duration of the study as well as to undergo additional pregnancy testing during the study.
- Subject has a laboratory confirmed SARS-CoV-2 infection as determined by RT-PCR assay prior to enrollment.
- Subject has evidence of either mild or moderate COVID-19 illness of less than 7 days from first onset, with minimal baseline symptom severity based on patient-reported FDA scoring system defined as follows:
 - Subject presents with at least two common symptoms of COVID-19 from the following list: stuffy or runny nose, sore throat, cough, low energy or tiredness, muscle or body ache,

⁶Immunology tests: COVID-19 relevant immunology labs (see Appendix 12.1 for complete list). See footnote to Appendix 12.1 as certain labs will be sent to and resulted from outside lab facilities.

⁷Quantitative blood SARS-CoV-2 antibody testing: Blood samples will be used; any FDA-approved or commercial testing method will be acceptable.

⁸WHO 9-point scale: see description of secondary end points for details.

headache, chills or shivering, feeling hot or feverish, nausea, vomiting, diarrhea, shortness of breath with exertion (without supplemental oxygen requirement) with a score of 2 or higher; impairment in sense of smell or taste with a score of 1 or higher **OR**

- Subject presents with any (i.e., at least one) symptom of COVID-19 as defined above AND clinical evidence of moderate COVID-19 as defined by FDA guidance for industry (such as respiratory rate >20 breaths per minute, heart rate >90 beats per minute, with oxygen saturation >93% on room air at sea level).
- Subject presents with high-risk for COVID-19-related inflammation determined by at least one comorbidity, including obesity, diabetes, hypertension, stable heart disease, respiratory disease, and / or non-severe fatty liver disease.
- Subject's overall health condition is deemed as suitable to fully and safely participate in this trial as determined by the Investigator.

Exclusion Criteria:

- Any clinical signs indicative of severe or critical COVID-19 as defined by FDA guidance for Industry at the time, including SpO2 < 93% and / or oxygen requirement.
- Hospitalization for COVID-19, or consideration thereof.
- ICU level of care and / or non-mechanical / mechanical ventilation and / or oxygen supplementation at time of enrollment.
- Pregnant or breast-feeding subjects.
- Subjects who cannot swallow tablets.
- History of any pre-existing organ impairment, such as:
 - o Severe kidney disease (known or estimated GFR < 30 mL / minute) or on dialysis.
 - o Uncontrolled, clinically significant heart diseases such as arrhythmias, angina or heart failure as defined by AHA / ACC Grade C and D.
 - o Chronic respiratory disease requiring supplemental oxygen.
 - Moderate and severe hepatic impairment as defined by Child-Pugh scoring Class B and Class C
- Elevated liver function tests (determined by ALT, AST, GGT, or ALP >2 x upper limit of normal, and/or total Bilirubin > upper limit of normal).

- History of malignancy or immunodeficiency within the prior 5 years.
- Acute respiratory illness other than COVID-19.
- Active bacterial, viral or fungal infection (including HIV, hepatitis B, hepatitis C).
- While dosed with the IP, the taking of prohibited concomitant medication or the ingestion of food that interferes with the IP, including:
 - Non-COVID19-related anti-viral medication such as lopinavir, ritonavir, ribavirin or interferon-1β.
 - Systemically administered immunosuppressive and anti-inflammatory agents, other than background standard of care for COVID-19 at the time.
 - Drugs and foods that are potent inhibitors or inducers of CYP3A4 and / or P-gp, as listed in FDA "Drug Development and Drug Interactions: Table of Substrates, Inhibitors and Inducers", including herbal medications such as St. John's Wort within 30 days or 5 half-lives (whichever is longer) prior to the first dose of study drug.
- Any other diseases or medical conditions or concomitant medications that are deemed as not compatible or appropriate for the subject's ability to fully and safely participate in this trial as determined by the Investigator.

Discontinuation Criteria and Early Termination Procedures

Subjects may withdraw voluntarily from participation in the study at any time and for any reason. Subjects may also be withdrawn on the basis of the Investigator's clinical judgment. This study may be terminated at the discretion of MedStar Health or of any regulatory agency for reasons including safety and/or treatment effect.

For enrolled subjects we anticipate that the main reasons for discontinuation of therapy will be either withdrawal of consent for continuation in the study or inability to tolerate the study. Other instances may include patient death, inability to take the study drug from severity of illness or inhospital complexity of illness. Subjective intolerance of the drug from minor side effects or alternatively cessation of COVID-19 related symptoms well ahead of the 28-day schedule may cause patients to want to discontinue the drug. With regards to drug toxicity itself, we anticipate minor symptomatology from adverse effects, such as headache, dizziness, nausea and vomiting, abdominal discomfort and rash (see also 1.4) based on prior human trial experience with the study drug. Should any subject dosed on the study drug experience seizures, which was reported as an

unrelated adverse event in an epilepsy trial, that individual would be subject to discontinuation out of an abundance of caution. Any emergent symptom that has no clear cause will result in a hold on subsequent study drug dosing until protocol assessment by the Study Investigator. The reasons for discontinuation of study drug will be documented clearly. In all cases study protocol monitoring will continue for the entire 60 days of the protocol as long as the subject stays consented.

When a subject withdraws or is withdrawn before completing the study, the date and reason for withdrawal are to be documented. Subjects who withdraw or who are withdrawn prematurely are to attend an early termination, at which time they will complete all assessments as outlined in the Schedule of Events (Table 1); moreover they will be encouraged to stay enrolled so that further safety and outcome information can be collected and analyzed.

In the event that a subject is withdrawn prematurely due to an adverse event or serious adverse event, the adverse event or serious adverse event will be followed until it resolves or stabilizes, or until it is judged by the Investigator to be no longer clinically significant.

5.4 Concomitant and Prohibited Medication

At time of enrollment, and at any point during the study, medication or the ingestion of food that interferes with the IP would preclude participation in the study, including:

- Non-COVID19-related anti-viral medication such as lopinavir, ritonavir, ribavirin or interferon-1β.
- Systemically administered immunosuppressive and anti-inflammatory agents, other than background standard of care for COVID-19 at the time.
- In vitro studies suggest that CYP-mediated metabolism is not a major route of clearance for belnacasan (VX-765/RVT-201/MSR-001) or VRT-043198. However, belnacasan (VX-765/RVT-201/MSR-001) was metabolized by CYP3A4 in a recombinant enzyme system.
- Drugs and foods that are potent inhibitors or inducers of CYP3A4 and / or P-gp, as listed in FDA "Drug Development and Drug Interactions: Table of Substrates, Inhibitors and Inducers", including herbal medications such as St. John's Wort within 30 days or 5 half-lives (whichever is longer) prior to the first dose of study drug
- Subjects should also be advised against the consumption of grapefruit juice since it is a known inhibitor of CYP3A.

6 MATERIALS

6.1 Study Drugs

All study medication will be managed by the MedStar Health Research Pharmacy (RP). The Pharmacy will store and dispense medication to subjects.

For all enrolled subjects, the first dose of study drug will be given orally only after the participant has documented consent, has completed screening and been verified to meet enrollment criteria. This screening visit may occur over more than one day if confirmatory PCR testing is needed. Subjects will be closely monitored for at least 30 minutes to assure they do not experience any untoward effect.

For outpatient subjects (and discharged former inpatient subjects), subjects will be instructed to take subsequent doses at 0600, 1400, 2200 (+/- 4 hours). They will self-record administration in a subject diary (see Appendix) to be reviewed by the study team who will assess compliance at each visit. The study team, under direction of the Investigator, will provide any needed medication education, including adequate storage requirements, with the subject and any relevant family member(s) or caretaker.

For subjects who become inpatients over the course of the trial, study medication will be supplied to the unit in which subjects are admitted and will be dosed by clinical nursing, recorded in the electronic medical record, and overseen by the study team. Doses will be given at 0600, 1400, 2200 (+/- 4 hours). Those who cannot swallow tablets will receive crushed tablets suspended in water and immediately administered through a nasogastric tube, by hospital nursing staff. At discharge and subsequent outpatient visits, enough medication will be dispensed to the subject to assure they have adequate supply until their next on-site follow-up visit.

6.2 Storage, Dispensing and Reconciliation of Study Drug and Identity of Investigational Products

All study medication will be stored at room temperature until dispensed. Storage within the RP is locked and secure, accessible only to investigational pharmacy staff. Storage condition temperatures are recorded 24 hours a day, 7 days a week, and 365 days per year and the RP is immediately made aware of any temperature excursions. In such an event, study medication will not be utilized until MedStar Health provides further direction. It is the Investigator's responsibility to ensure that accurate records of study medication dispensation and administration

are maintained. The RP will support the Investigator in medication accountability and dispensation tracking, they have a clear process for return and destruction of investigational medications.

Table 2: Identification of Investigation Product

Product Name	Belnacasan (VX-765/RVT-201/MSR-001)				
Dosage form Tablet containing 300mg of API					
Route/dosage	oute/dosage Oral				
Dosing Instructions Three tablets, three times per day (0600, 1400, 2200 +/- 4 hours					

Product Name	Placebo
Dosage form	Tablet containing 0mg of API
Route/dosage	Oral
Dosing Instructions	Three tablets, three times per day (0600, 1400, 2200 +/- 4 hours)

7 STUDY PROCEDURES

7.1 Observations and Measurements

Subject informed consent must be obtained prior to conducting any study-specific procedures. The informed consent can be signed by the subjects' legally authorized representative (LAR) if necessary. The Investigator will assure that each subject/LAR is adequately consented to the requirements of participation including the potential risks and benefits and voluntary nature of the trial that he or she is free to discontinue participating in the study at any time. The subject/LAR will be given the opportunity to ask questions and allowed adequate time to consider the information provided. All assessments and procedures will be completed according to the Schedule of Events. A custom subject diary has been developed for this study. The diary will be tested for basic comprehensibility before finalizing and using with subjects. The study teams may consent subjects by remote consent process that may include the use of an e-consent platform, Interlace, for documentation of consent if they are no longer at a MedStar site. In this circumstance initial contact will be made with potential subjects via telephone to discuss the trial followed by any subsequent discussions needed to assure consent is obtained per Institutional policy and procedure, as approved by the IRB. The study team will communicate with the home health agency directly to schedule the collection of the RT-PCR and screening labs, once consent is obtained, for a time that is convenient to the subject. Following collection, the agency will transport these tests to MedStar Georgetown University Hospital for resulting. Once eligibility is confirmed by PCR the

subject will return to either MedStar Washington Hospital Center or MedStar Franklin Square to complete the remainder of the screening/enrollment visit.

7.2 Instructions to Subjects

At enrollment, the Study Team will explain the subject diary (see Appendix) and ensure they understand what to enter in each field. They will be told about the importance of collecting the information in the diary for scientific purposes, and that even if they discontinue intake of the study drug, they should continue to participate in the study, continue to fill in the diary, and continue to attend planned study visits.

For outpatient subjects (and discharged former inpatient subjects), subjects will be instructed to take 3 tablets of IP at 0600, 1400, 2200 (+/- 4 hours) for up to 28 days. They will self-record administration of the IP in the subject diary to be reviewed by the study team who will assess compliance at each visit. The study team, under direction of the Investigator, will provide any needed medication education, including adequate storage requirements, with the subject and any relevant family member(s) or caretaker.

For subjects who become inpatients over the course of the trial, study medication will be supplied to the unit in which subjects are admitted and will be dosed by clinical nursing, recorded in the electronic medical record, and overseen by the study team. Doses will be given at 0600, 1400, 2200 (+/- 4 hours). Those who cannot swallow tablets will receive crushed tablets suspended in water and immediately administered through a nasogastric tube, by hospital nursing staff. As study medication will be administered by hospital staff, and there are no specific instructions to subjects. At discharge and subsequent outpatient visits, enough medication will be dispensed to the subject to assure they have adequate supply until their next on-site follow-up visit.

Women with a history of menstruation must agree to use effective method of contraception and protections that align with International Council on Harmonization M3 R2 guidelines for highly effective methods of contraception for the duration of the study (i.e., two forms of contraception, whereby one result in a less than 1 percent per year failure rate when used consistently and correctly), as well as to undergo additional pregnancy testing during the study on day 14. Details of all pregnancies in female participants will be collected for 60 days after randomization.

Warnings and Precautions

Subjects will be watched carefully for signs of previously documented symptoms in human patients that have received belnacasan (VX-765/RVT-201/MSR-001), as well as symptoms to indicate a drug reaction or new symptoms that could be temporally attributable to the drug. The most frequent adverse effects in humans have been mild and mainly include headache, nausea, lethargy and dizziness. No serious side effects have been described in human and animal studies.

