For this trial we will treat for a maximum of 28 days. Our rationale for this timeframe is that while there is an expectation that the illness lasts up to 12-15 days in those who recover without complication, others will endure a longer duration, and some will experience persistent, new onset or worsening disease related symptoms. A recent study from the Centers for Disease Control and Prevention (https://www.cdc.gov/mmwr/volumes/70/wr/mm7017e3.htm?s cid=mm7017e3 w) found that among 3,171 non-hospitalized adult COVID-19 patients, 69% had one or more outpatient visits 28–180 days after the diagnosis. Two thirds had a visit for a new primary diagnosis, and approximately one third had a new specialist visit. Symptoms potentially related to COVID-19 were common new visit diagnoses. Visits for these symptoms decreased after 60 days but for some patients continued through 120–180 day. Furthermore, some individuals develop sequela that are likely related to post-viral immune dysregulation in the first few months albeit there is little known about this group. Though we are unlikely to learn about the effect of the drug in this latter population we do need to establish safety for a duration that includes the other groups mentioned above.

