3.2 Primary Endpoint

Incidence of Adverse Events and Serious Adverse Events assessed out to day 60.

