7.9 Reporting Requirements

Any adverse event, defined below, that begins any time between the start of the first dose and

within 28 days after the end of the last dose are to be recorded on the appropriate CRF and in detail

in the source documentation (preferably the electronic medical record directly).

Adverse Event: Any untoward medical occurrence in a subject administered a pharmaceutical

product, which does not necessarily have to have a causal relationship with this treatment. An

adverse event can be any unfavorable sign (including an abnormal laboratory finding), symptom,

or disease temporally associated with the use of the investigational drug, whether or not considered related to the investigational drug.

Serious Adverse Event: An untoward event or reaction that at any dose:

- results in death
- is life-threatening
- results in hospitalization or prolongs existing hospitalization
- results in permanent or significant disability or incapacity
- requires intervention to prevent permanent impairment/damage
- results in congenital anomaly or birth defect

In addition, any important medical event that may not result in death, be life-threatening, or require hospitalization may be considered serious when, based upon appropriate medical judgment, they may jeopardize the patient or subject and may require medical or surgical intervention to prevent one of the outcomes listed in this definition.

Life-threatening: An event which a subject was at risk of death at the time of event. There is a distinction between the severity and the seriousness of an adverse event. Severity is a measurement of intensity, thus a severe reaction is not necessarily a serious adverse event. For example, a headache may be severe in intensity, but would not be serious unless it met one of the criteria for serious adverse events listed previously.

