7.10 Serious Adverse Events

Adverse events (AEs) and serious adverse events (SAEs) will be collected from the time the first dose of IP is administered until 28 days after the last dose of IP. Medical occurrences that began prior to the start of study treatment, but after obtaining informed consent will be captured as Medical History/Current Medical Conditions on the CRF. The Investigator or site staff will be responsible for the identification and documentation of events meeting the criteria and definition of an adverse event or serious adverse event, as provided in the study protocol. SAEs assessed as related to study participation (e.g., dosing, protocol mandated procedures, invasive tests, or change in existing therapy) or related to a concomitant medication will also be captured once the subject has taken the first dose of study medication.

In the event of an AE or SAE, it will be the responsibility of the Investigator to review all documentation (e.g., hospital progress notes, laboratory, and diagnostics reports) relative to the event and attempt to establish a diagnosis of the event based on signs, symptoms, and other clinical information. Once the Investigator becomes aware that an SAE has occurred, they are to report the information to MedStar Health within 24 hours and provide an assessment of causality.

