9 ESTIMATED DURATION OF THE STUDY

This study has an estimated maximum duration of up to 8.5 weeks for each subject. The study duration from first subject enrolled to last subject enrolled is expected to be 3-6 months.

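### Pregnancy follow-up stops at day 60 and SAE collection at about day 56, so the planned follow-up cannot ascertain the birth outcome of an exposed pregnancy, although birth defect is a listed SAE criterion

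*Combined protocol and SAP*

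**What the plan says.** Four parts of the protocol bear on this.

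- **Pregnancy data (7.2).** After the contraception and pregnancy-testing requirements, the section says: "Details of all pregnancies in female participants will be collected for 60 days after randomization".
- **SAE definition (7.9).** One of the criteria is an event that "results in congenital anomaly or birth defect".
- **Collection window (7.9 and 7.10).** Under 7.9, events that begin between the first dose and "within 28 days after the end of the last dose are to be recorded on the appropriate CRF". Under 7.10, AEs and SAEs are collected from the first dose "until 28 days after the last dose of IP".
- **Length of dosing and follow-up.** Section 1.3 states: "For this trial we will treat for a maximum of 28 days". Section 9 states: "This study has an estimated maximum duration of up to 8.5 weeks for each subject". The primary endpoint in 3.2 is "Incidence of Adverse Events and Serious Adverse Events assessed out to day 60". The Schedule of Events (Table 1 in 5.2) has no contact after day 60.

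Entry rules limit when an exposed pregnancy could begin. Section 5.3 excludes "Pregnant or breast-feeding subjects", and 7.7 requires a negative serum test before women of child-bearing potential enter.

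**The concern.** The protocol treats exposure in pregnancy as a risk. It asks for two contraceptive methods, tests for pregnancy at entry and again during the study, and defines a birth defect as serious. If a pregnancy occurs, however, the only rule specific to it stops after 60 days, and the general SAE window closes slightly sooner. The protocol can therefore detect an exposed pregnancy but has no planned step for learning how it ended.

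Safety is the primary objective, and the drug has no approved use (1.2). One exposed pregnancy with a known outcome would be useful information. It is hard to recover afterwards if neither consent nor contact was arranged in advance.

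**Working it through.** The plan gives no figure to reproduce on this point, so the check is calendar arithmetic followed by a comparison of sections.

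**Inputs from the protocol**
- Dosing for at most 28 days (1.3).
- AE/SAE collection to 28 days after the last dose (7.9, 7.10).
- Pregnancy details to day 60 (7.2).
- 40 subjects, 20 per arm (8.7).
- At least one contraceptive method with failure below 1% per year (7.2).

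**Assumptions not in the documents**
- Conception between day -14 (missed by the entry test) and day 28 (last dosing day).
- Term birth at 37 to 40 weeks and a very preterm birth at 24 weeks, both counted from the last menstrual period, which is taken as 14 days before conception.

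**Step 1. When collection ends**
- AE/SAE window: 28 + 28 = day 56 with full dosing, and sooner if dosing stops early.
- Pregnancy details: day 60.

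**Step 2. Gestational age at day 60**

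Formula: (60 - conception day + 14) / 7 weeks.
- Conception day -14: 88 / 7 = 12.6 weeks.
- Conception day 0: 74 / 7 = 10.6 weeks.
- Conception day 28: 46 / 7 = 6.6 weeks.

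**Step 3. Study day of birth**

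Formula: conception day + 7 x gestational weeks - 14.

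| Conception day | Birth at 24 weeks | Birth at 37 weeks | Birth at 40 weeks |
|---|---|---|---|
| -14 | 140 | 231 | 252 |
| 0 | 154 | 245 | 266 |
| 28 | 182 | 273 | 294 |

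The earliest birth in the table is day 140. That is 140 - 60 = 80 days after pregnancy collection ends and 140 - 56 = 84 days after SAE collection ends. For term births the gap to day 60 runs from 231 - 60 = 171 days to 294 - 60 = 234 days.

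**Step 4. How many pregnancies to expect**

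Take failure at 1% per year and, as an upper bound, treat every subject as a woman of child-bearing potential.
- All 40 subjects over 60 days: 40 x 0.01 x 60/365 = 0.07.
- The 20 belnacasan subjects over 60 days: 20 x 0.01 x 60/365 = 0.03.
- The 20 belnacasan subjects over 28 days of dosing: 20 x 0.01 x 28/365 = 0.015.
- With failure ten times worse (10% per year), the 60-day figures are about 0.7 for 40 subjects and 0.3 for 20.

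**Step 5. Does any other section extend the follow-up?**
- 5.3 follows an event until it resolves or stabilizes, but only where that event led to the subject's withdrawal.
- 7.8 asks that subjects with an AE be followed to determine outcome. It does not name pregnancy as an AE.
- 5.1 and 8.1 describe 60 days as a minimum for data collection, but neither adds a pregnancy procedure.

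**The case against.** The strongest opposing case has six parts.

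1. **Section 7.8 has no day limit.** A positive pregnancy test could be flagged as clinically significant, which 7.7 makes an adverse event by definition, and 7.8 would then require follow-up to outcome. This route is arguable but not clear: pregnancy is nowhere named as an AE, the sentence specific to pregnancy sets 60 days, and a defect found at birth would be a new event outside the window in 7.10. Section 7.9 sets its window by when an event begins, so a malformation formed early in gestation might be said to fall inside it. That would settle how to classify a known defect, not how anyone would learn of it.

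2. **Reporting duties carry no date of their own.** The 24-hour report in 7.10, the sponsor's regulatory reporting in 7.11, the IND safety reports in 7.12 and the DSMB's review of SAEs in 7.14 arguably apply to any event that becomes known. This stands. What is missing is planned, active ascertainment, not every reporting route.

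3. **The SAE definition is a general list.** Naming a criterion does not commit the trial to observe it, and the primary endpoint is openly limited to day 60. This is fair, and it is why the point is not a flaw in the endpoint.

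4. **The sentence in 7.2 may mean pregnancies that begin within 60 days.** Even so, no follow-up to outcome is stated and SAE collection still closes near day 56.

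5. **Other documents may cover it.** Consent pages were removed from the text available for review, and the DSMB charter and CRF guidelines are separate documents. They may say more, but the protocol's own rule would still need to agree with them.

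6. **Almost no pregnancies are expected.** This stands and sets the severity.

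A reader might infer that a congenital anomaly could never be observed, or that the trial would report none whatever happened. The documents do not support that. An anomaly found in an early loss or on an early scan before day 60 could be recorded, and one reported spontaneously later could still be passed on.

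**Conclusion.** The point holds in a limited form. As written, the planned follow-up cannot ascertain the birth outcome of a pregnancy exposed to study drug, because both collection windows close well before any birth. This does not depend on fine assumptions about gestation, since the most favourable combination examined still leaves a gap of 80 days. It does assume that no document outside the supplied text extends the follow-up.

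Severity is minor. Well under one pregnancy is expected if contraception is used as required, and anomalies would be a small fraction of that. The primary analysis, the safety decision rule, power and alpha are unaffected. The change is worth making because it closes a gap in safety capture at very little cost.

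**What to change.** - **7.2:** replace the 60-day limit with collection of the outcome of any pregnancy conceived before or during dosing with study drug, or within the study's contraception period. Collect it by telephone or from records, with the participant's consent.
- **7.9 and 7.10:** state that a congenital anomaly or birth defect from such a pregnancy is recorded and reported as an SAE whenever it becomes known, regardless of the general window.
- **Analysis:** keep the day-60 cut-off and report these outcomes as narratives.

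The cost is about two protocol sentences and one line in the consent form. The downside is a few contacts or a records request per pregnancy after the last visit, most likely for no subjects at all.
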